9.7.2.2 Primary Analysis

The number of participants in each treatment group and total amount of follow-up time per treatment group will be reported and compared to enrolment targets (1000 participants per group). If a sufficient number of participants treated with lasmiditan is enrolled, a comparative analysis will be executed as part of the final analysis (See 9.7.2.3 for Additional Analyses).

If the required sample size is not achieved to provide meaningful comparison between Lasmiditan Group and comparator groups (Other Acute Medication Group and No Acute Medication Group), unadjusted incidence rates of MVAs in each treatment group with precision estimates will be provided as primary analysis (see Sections 9.5 and 9.7.2.2.2.2) and descriptive statistics will summarise participant characteristics, treatment patterns, driving patterns, and self-reported MVA experience through the 12-months of the follow-up period.

9.7.2.2.1 Primary Analysis Population

Unless otherwise stated, analyses will be performed on all participants who have given informed concent and completed at least the baseline online survey and the first follow-up online survey 30 days after baseline. To align with the primary research objective, the first occurrence of MVA since study enrolment will serve as the outcome of interest for primary analysis.

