9.1 Study Design

This is an observational cohort study, aiming to compare the one-year risk of MVA associated with three treatment strategies of interest, in patients with migraine in the US. The comparative treatment strategies of interest, as well as other core elements of the study design, are described in Table 1. No visits, examinations, laboratory tests, or procedures are mandated or recommended as part of this study.

Eligibility Criteria	 Participant age is 18 to 74 years old at enrolment; Participant has a valid driver's licence that they received ≥1 year before enrolment; Participant has access to a vehicle at the time of enrolment and anticipates having access to a vehicle for the next 12 months (at enrolment); Participant must confirm having driven at least once during the 6 months prior to enrolment; Participant must provide informed consent to participate in this study; Participant must be able to read and understand English; Participant must currently reside in the US; Participant must have access to a personal device with internet connection; Willing to complete study surveys once every 30 days for 12 months at enrolment; and Participant must be willing to provide consent to access their antimigraine medication prescription claims data from ExamOne ScriptCheck and allow HCP to confirm migraine diagnosis, completing the Health Insurance Portability and Accountability Act of 1996 (HIPAA) Authorisation/Medical release Form.
Treatment strategies	 Use of lasmiditan exclusively or in conjunction with other acute antimigraine migraine medication for up to one year; Use of any non-lasmiditan prescribed acute anti-migraine medication (see medications list in Annex 3) for up to one year; and No use of any prescribed acute anti-migraine medication for up to one year. Self-reported use of prescribed acute anti-migraine medications will be utilised to assign treatment exposure category. The self-reported use of prescribed preventive anti-migraine medication will not be considered for treatment group classification

Table 1.Core Study Elements for The Primary Analysis using a 'Nested Trial'
Approach

Outcome	Self-reported first occurrence of MVA for which the participant was the driver since study enrolment.

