9.3.4 Follow-up Variables

The following additional variables will be collected every 30 days during a 12-month period of follow-up for analysis of the primary and secondary objectives:

Dynamic eligibility variables

- Possession of an active driver's licence over the past 30 days,
- Access to a motor vehicle over the past 30 days,
- Have driven at least once in the previous 30 days, and
- Resides in the US over the past 30 days.

Medication use, migraine experience, and the use of anti-migraine medication in the past 30 days

- Migraine experience over the past 30 days: number of migraine attacks, impact of migraine on daily life),
- Use of acute and preventive anti-migraine medications over the past 30 days (medications names, dose for lasmiditan),
- Use of concomitant medications potentially associated with MVA risk (including antihistamines, antidepressants, benzodiazepines, beta-blockers, opioids, anti-seizure medications, antipsychotics, sleeping pills including sedatives and hypnotics) within the last 30 days, and
- New comorbidities declared in the last 30 days (including hypertension, hypotension, musculoskeletal diseases, ophthalmological diseases, insomnia, anxiety, diabetes, depression, other psychiatric disease, chronic insomnia, chronic fatigue syndrome, seizure disorders).

Driving characteristics and experience of MVAs for which the participant was the driver

- Change of ZIP code of residency,
- Approximate number of miles driven in the past 30 days, and
- Number and dates of self-reported MVAs for which the participant was the driver occurring during the past 30 days, details and circumstances of these MVAs (details provided below).

Details on self-reported MVAs for which the participant was the driver in the last 30 days

- Location of MVA,
- Severity of the accident (approximated by the extent of motor vehicle and property damages),
- Speed of the motor vehicle driven by the participant,
- Other vehicle(s) and/or persons involved (i.e., pedestrian, cyclist, motorcyclist, car, other vehicle),

Non-Interventional Protocol

- Perceived fault and reasoning for the accident,
- Seriousness of related injuries for any persons involved in the MVA:
 - Slightly injured: minor character of injury not requiring medical treatment such as a sprain (including neck whiplash injury), bruise or cut which are not judged to be severe, or slight shock requiring roadside attention, and

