9.3.5 Additional Contact

In the event that participants do not respond to two consecutive survey invitations, the alternative contact provided as part of profile creation may be contacted. The following information will be solicited from the alternative contact:

- Vital status of the study participant,
- (If deceased) Cause of death for the study participant, including whether it was related to an MVA, and
- Hospitalisation or serious injury related to MVA for the driver.

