- 2. It may not be possible to achieve balance between all potential confounders across treatment groups (i.e., ASMD<0.1). Imbalances in baseline characteristics will be addressed with a re-specification of inverse probability weights (e.g., Changing the functional form of the variable or including interaction terms). However, if imbalances remain these will be described along with their potential impact on the outcome estimate(s).
- 3. It may not be possible to model all collected covariates due to sparsity, collinearity, or other factors that can preclude convergence of statistical models. For this reason, the final variables and functional forms of the baseline (L_0) and time-varying (\overline{L}_k) covariate vectors described in the models above will be determined at the time of analysis.
- 4. The time interval of the analysis, denoted 'k', directly influences the dimensionality of the dataset, and concequent computational intensity of the analysis. Particularly, choosing a time interval of one day will greatly increase the number of rows in the analytic data set and, concequently, increase the computation time of nonparametric bootstrap algorithms for standard error estimation. Therefore, if computation times are too great then the time interval of the analysis may be expanded accordingly (e.g., to one week or one month).

9.7.2.2.2.3 Missing Data

Missing data may arise from participants who skip a single survey only, or who are lost to followup (defined as non-responce on two concecutive follow-up surveys). Participants who are lost to follow-up will be censored at 67 days following the opening of their last survey (as participants are allotted 7 days to answer each 30-day survey). Missing data arising from non-response will be addressed using *last observation carried forward*, where the most recent survey responses are "carried forward" under the assumption that participants' treatment and confounder histories did not change during the time spanning from the participant's final response through the period of non-response.

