9.9.5 Missing Data and/or Dropout

Missing items will not be permitted by the online survey and so intermittent missingness is not expected. Anticipated missing data could be due to participants exiting the questionnaire before completion and as for any longitudinal study, attrition and loss-to-follow-up may occur. However, participants may not complete all surveys included as part of the study design (e.g., every 30 days for 12 months).

It could also happen that a participant has a very serious/severe accident and due to injuries or death, information will not be known/reported for the study, which could lead to underestimation of MVA incidence. This will be mitigated by requiring participants to designate an alternative contact who can confirm information if the participant is unable to be reached (see Section 9.3.5 for details of what may be requested from the alternative contact) Missing data arising from non-response will be addressed using *last observation carried forward*, (See Section 9.7.2.2.2.3).

10. Protection of Human Subjects

This study will be submitted to at least one ethical review board (ERB) for review and to confirm that the study is considered non-interventional. Regulatory authorities will be notified and approval sought as required by local laws and regulations. This observational study will be performed in accordance with ethical principles that are consistent with the Declaration of Helsinki (WMA 2013), the ICH guideline E6R1 (International Council for Harmonisation 1996) and the Good Pharmacoepidemiology Practices (GPP) issued by the International Society for Pharmacoepidemiology (ISP 2015) and the applicable legislation on non-interventional studies and/or observational studies.

11. Management and Reporting of Adverse Events/Adverse Reactions

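### The primary population requires the first follow-up survey, so a crash that prevents that survey drops out; later severe crashes and unsurveyed time are not properly tied to the outcome

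*Protocol*

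**What the plan says.** - **Start and outcome.** Table 1 (Protocol 9.1) starts follow-up at the baseline survey. The outcome is "Self-reported first occurrence of MVA for which the participant was the driver since study enrolment".
- **Population.** Section 9.7.2.2.1 admits, unless otherwise stated, those who consented and "completed at least the baseline online survey and the first follow-up online survey 30 days after baseline".
- **Non-response.** Loss to follow-up means two consecutive missed surveys (Table 1; 9.2.4.4; 9.7.2.2.2.3). "Participants who are lost to follow-up will be censored at 67 days following the opening of their last survey". A single skipped survey is handled by last observation carried forward, which 9.7.2.2.2.3 justifies for treatment and confounder histories only. Section 9.7.2.2.2.1 sets the event indicator to 0 at censoring.
- **Recall window.** Each follow-up survey collects "Number and dates of self-reported MVAs for which the participant was the driver occurring during the past 30 days" (9.3.4).
- **Severe crashes.** Section 9.9.5 accepts that a very serious accident may go unreported, "which could lead to underestimation of MVA incidence", and continues: "This will be mitigated by requiring participants to designate an alternative contact who can confirm information". Under 9.3.5, after two missed surveys "the alternative contact provided as part of profile creation may be contacted". That person is asked about vital status, cause of death (including any link to an MVA) and "Hospitalisation or serious injury related to MVA for the driver".
- **Deferral.** Section 9.6.4 leaves endpoint assessment of lost participants to the SAP.

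**The concern.** Entry to the primary analysis depends on something that happens after time zero and that the outcome itself can prevent. The crashes most likely to be lost are the severe ones, which matter most in a safety study. The protocol recognises the problem and names a remedy, but does not connect that remedy to the outcome definition or collect all the items needed to use it.

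Separately, person-time is counted in periods where no completed survey could have recorded an MVA, which lowers every incidence rate. This would matter most directly if lasmiditan recruitment falls short, because unadjusted incidence rates then become the primary analysis (9.5, 9.7.2.2).

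**Working it through.** **1. The plan's own figure.** Inputs from 9.5: 3% comparator risk, HR 2.0, 80% power, 5% level (two-sided assumed).
- Freedman events: (1.960 + 0.842)² × ((1 + 2)/(1 − 2))² = 70.64.
- Lasmiditan risk: 1 − 0.97² = 5.91%. Mean risk: 4.455%.
- N per group: 70.64/(2 × 0.04455) = 792.8, so 793. With 20% dropout: 793/0.80 = 991.25, so 992.

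Both stated figures reproduce and are not in dispute. They supply the hazards used below.

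**2. The population rule against the non-response rules.** Take a participant who skips survey 1 and answers survey 2. Table 1 and 9.7.2.2.2.3 keep that person, because only one survey was missed. Section 9.7.2.2.1 excludes them. Now take a driver killed on day 20. Survey 1 is never answered, so the participant is outside the population even if the alternative contact later confirms the crash.

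**3. Size of the first-survey exclusion.** Yearly hazards are −ln(0.97) = 0.03046 and twice that, 0.06092. First MVAs in 30 days per 1000:
- at 3% risk: 1000 × (1 − exp(−0.03046 × 30/365)) = 2.5;
- at 5.91% risk: 1000 × (1 − exp(−0.06092 × 30/365)) = 5.0.

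Only crashes that stop the participant answering within the 7-day survey window are lost. The documents give no figure for that share.

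**4. Size of the 67-day credit.** The 67 days are 2 × 30 + 7. If all of the 20% dropout in 1000 participants were survey non-response, the credit is 200 × 67/365 = 36.7 person-years. With dropouts averaging half a year (assumption), observed time is 800 + 200 × 0.5 = 900 person-years, so the extra is 36.7/900 = 4.1%. At the two hazards, about 1.1 and 2.2 MVAs would be expected in that time. The 4.1% is an upper bound:
- withdrawal is a separate end of follow-up;
- participants who miss survey 1 are excluded;
- the one-year limit shortens the credit for late dropouts.

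**5. A single skipped survey.** A participant answers at day 30, skips day 60 and answers at day 90. The day-90 survey asks about roughly days 60 to 90. No survey asks about days 30 to 60, which remain at risk.

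**6. What differential loss would do.** Let s be the share of MVAs lost in each group. The apparent HR is 2.0 × (1 − s_las)/(1 − s_comp). Events are 793 × [0.03(1 − s_comp) + 0.0591(1 − s_las)]. Power is Φ(√events × (HR − 1)/(HR + 1) − 1.96). All shares below are assumptions.

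| Loss, comparator / lasmiditan | Events | Apparent HR | Power |
|---|---|---|---|
| 0% / 0% | 70.7 | 2.00 | 80% |
| 10% / 10% | 63.6 | 2.00 | 76% |
| 0% / 10% | 66.0 | 1.80 | 64% |
| 5% / 20% | 60.1 | 1.68 | 51% |

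The 67-day credit alone has a smaller effect. With f = d(67/365)/(1 − 0.5d), assumed dropout d of 30% on lasmiditan gives f = 6.5%, and 10% to 15% on comparator gives 1.9% to 3.0%. The HR is then multiplied by 1.019/1.065 to 1.030/1.065, that is 0.96 to 0.97.

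**7. Whether the weights help.** The censoring weights in 9.7.2.2.2.2 condition on treatment and covariate history. They cannot correct loss caused by a crash that was never recorded.

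**The case against.** A reader might infer that no crash that silences a participant can ever count as an outcome. The documents do not say that. Section 9.9.5 offers the alternative contact as the remedy for underestimated incidence, 9.3.5 collects MVA-related death, hospitalisation and serious injury, and 9.6.4 leaves endpoint handling of lost participants to the SAP, which is not at hand. Nothing bars a contact-reported MVA from being an event. After the first survey this is unreconciled wording, not an exclusion.

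Two other strong readings also fail. A participant injured in month 1 is not lost if able to answer while the survey is open. And the 67 days apply only after two consecutive missed surveys, not to every non-responder.

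It is also fair that the numbers are small at average hazards, that equal loss leaves the hazard ratio unchanged, and that a factor of 0.96 to 0.97 is minor beside the protocol's own interval of 1.29 to 3.10 at 1000 per group (Table 3).

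What the objection does not remove: 9.7.2.2.1 already fixes the population, and 9.7.2.2.2.3 already fixes the censoring day. The recall window and the contact's questions are data collection. If the crash date, the driver status of a death or the skipped month is never asked about, no SAP can recover it.

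**Conclusion.** The point holds in limited form. Exclusion is certain only for crashes that prevent the first follow-up survey, and there 9.7.2.2.1 also contradicts the protocol's own treatment of one missed survey. For later severe crashes, the self-reported outcome and the alternative-contact mitigation must be reconciled, and the contact items are incomplete for a dated driver outcome. Unsurveyed time is counted as at risk after two missed surveys, and an MVA in a singly skipped month is not asked about.

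The average effect is modest: at most about 4% extra person-time, and only the incapacitating fraction of about 2.5 to 5 first MVAs per 1000 in the first 30 days. These figures rest on the protocol's 3% risk and HR of 2.0, a constant hazard, and all dropout being survey non-response. Bias in the hazard ratio needs loss that differs by group, and its size is an assumption. The protocol should be corrected, but the defect does not by itself invalidate the comparison.

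**What to change.** 1. Define the primary population as all who complete the baseline survey.
2. State that driver MVAs reported by the alternative contact count as outcome events. Add the MVA date to the contact's questions and, for deaths, whether the participant was driving.
3. After a skipped survey, ask about MVAs since the last completed survey.
4. End at-risk time at the last completed survey unless an event is confirmed. Do not credit event-free time to day 67 on the contact's word: that person is asked only about death, hospitalisation and serious injury, so minor MVAs would still be missed.
5. State that the censoring weights do not correct loss caused by an unrecorded crash.

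Steps 1, 2 and 4 belong together. A participant with only a baseline survey and no confirmed event contributes no time under step 4, so step 1 restores lost crashes mainly through step 2.

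Cost: protocol wording, two contact questions and one changed date reference in the survey. Recall is somewhat longer after a skipped survey, and person-time falls slightly. Contact-confirmed events fall in time that others do not contribute, which pushes rates slightly upward, so report their number by group and repeat the analysis without them.

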9.7.2.2.2 Primary Statistical Analysis

9.7.2.2.2.1 Data Structure and Notation

The data structure generated from the procedure illustrated in Section 9.1 will take on the general form shown in Table 5. As illustrated, each row of the data will represent an observation of a given participant at the kth interval of follow-up for the mth 'trial.' The treatment indicator A_k will take on one of three values corresponding to the treatment strategies of interest (see Section 9.1) and will be constant for a given participant within a given mth trial. Treatment history, denoted A_{k-1} , is the treatment the participant received in the prior (k-1) interval. A vector of baseline covariates, denoted L_0 , will take on fixed values across all 'k' intervals of a given participant's 'participation' in an mth trial. A vector of time-varying covariates, denoted L_k , will take on their recorded values at time 'k' in a given participant-trial. The event indicator, denoted D_{k+1} , will take on a value of one if the event occurred in the subsequent (k+1) interval, or a value of 0 otherwise (e.g., censoring).

In the data structure, the number of rows for each participant in a given mth trial will correspond to the length of follow-up. For example, in Table 5, Participant 3 participated in nested trial 7 and nested trial 9. This participant was followed-up for four intervals in trial 9 and experienced the outcome event in the 4th interval of follow-up. Notably, treatment information recorded in the 4th interval of follow-up is discarded because it is unknown whether treatment was administered before or after the outcome event within that interval. This is because the surveys only collect information and treatment data at the 30-day level.

Participant ID	Trial No. (m)	Follow -up (k)	Treatment (A _k)	Treat Hx (A _{k-1})	Baseline Covariate (L ₀)	Time- Varying Covariate (L _k)	Outcome (D _{m+k+1})	Censor (C _{m+k+1})
1	45	0	0	0	0	0	0	0
1	45	1	0	0	0	1	0	0
1	45	2	0	0	0	0	0	1
2	34	0	2	2	1	0	0	0
2	34	1	2	2	1	1	1	0
3	8	0	1	1	0	1	0	0
3	8	1	1	1	0	0	0	1
3	9	0	0	1	1	0	0	0
3	9	1	0	0	1	0	0	0
3	9	2	0	0	1	1	1	0

 Table 5.
 Generalised Longitudinal Data Structure for the Final Analysis

9.7.2.2.2.2 Statistical Models

The crude (unadjusted) estimates of the number of incident MVAs, total person-time, and incidence rate of first occurrence of MVA since study enrolment under each treatment strategy will be presented. These figures will be calculated using the person-time-trial level analytic data set described in Section 9.7.2.2.2.1.

A marginal structural pooled logistic regression model will be fit to the data structure described in Section 9.7.2.2.2.1 to estimate the relative hazard of MVA between the Lasmiditan Group and the Other Acute Medication Group, as well as between the Lasmiditan Group and the No Acute Medication Group. Using the notation in Section 9.7.2.2.2.1, the model will take on the following form:

$$logit[pr(D_{m+k+1} = 1 | A_k, L_0, \overline{D}_{m+k} = 0, \overline{C}_{m+k+1} = 0)] = \beta_{0,m+k} + \beta_1^T A_k + \beta_2^T L_0$$

where $\beta_{0,m+k}$ is a time-varying intercept (i.e., a parametric estimation of the baseline hazard) that will include a spline or other polynomial function of follow-up interval 'k' and trial number 'm'; β_1 is a vector of the log hazard ratios of interest (comparing a reference treatment strategy to the remaining strategies); β_2 is a vector of coefficients of the baseline covariates. Under the rare disease assumption, the exponentiated β_1 coefficients will approximate a hazard ratio, provided the event rate within each 'k' time interval is <8%. This will be verified at the time of the analysis.

To adjust for potential confounding, stabilised time-varying inverse probability of treatment to weights will be estimated as follows:

$$SW_{m+t}^{A} = \prod_{k=m}^{m+t} \frac{f(A_{k}|\bar{A}_{k-1}, L_{0}, \bar{D}_{k-1} = 0)}{f(A_{k}|\bar{A}_{k-1}, L_{0}, \bar{L}_{k-1}, \bar{D}_{k-1} = 0)}$$

LY573144 Lasmiditan

Non-Interventional Protocol

Given that there are three comparator treatment strategies, the density in the numerator and denominator of this stabilised weights will be estimated using a multinomial regression model. Informally, the numerator of the weight is the probability of receiving the treatment that the participant actually received at time 'k,' conditional on treatment and baseline covariate histories and the denominator of the weight is the probability of receiving the treatment that the participant actually received at time 'k,' conditional on treatment, baseline covariate, and time-varying covariate histories.

Because participants are censored when they deviate from their assigned treatment strategies, selection bias may result. To account for this, inverse probability of censoring weights will be estimated as follows:

$$SW_{m+t}^{C} = \prod_{k=m}^{m+t} \frac{f(C_{k+1} = 0 | \bar{A}_k, \bar{C}_k = 0)}{f(C_{k+1} = 0 | \bar{A}_k, L_0, \bar{L}_k, \bar{C}_k = 0)}$$

The density in the numerator and denominator of this weight will be estimated using a logistic regression model. Informally, the numerator of the weight is the probability of being uncensored in the next interval conditional on treatment history and the denominator of the weight is the probability of being uncensored in the next interval conditional on treatment, baseline covariate, and time-varying covariate histories.

Observations in the marginal structural pooled logistic model specified above will be weighted by the joint density of the two weights as follows:

$$SW_{m+t}^{A,C} = SW_{m+t}^A \times SW_{m+t}^C$$

Observations in this analysis are not independent due to the use of weighting and allowance of repeated entry into the analytic cohort (i.e., through participation in more than one nested trial). To account for this lack of independence, nonparametric bootstrap will be used to estimate standard errors and confidence intervals.

A weighted and unweighted table of baseline characteristics will be generated using the persontime-trial level data set described in Section 9.7.2.2.2.1. Absolute standardised mean differences (ASMD) will be used to evaluate imbalances in these characteristics between participants assigned to the lasmiditan treatment strategy vs. the remaining two treatment strategies. ASMDs of the <0.1 will be considered imbalanced.

Contingencies:

1. The joint density of the inverse probability weights $SW_{m+t}^{A,C}$ may contain extreme values if there are few patients in the study sample that possess a particular combination of characteristics within each level of treatment strategy and time interval. If this occurs, weights will be incrementally truncated at upper and lower P^{th} percentile (e.g., 99.9th, 99.8th, 99.7th percentiles, etc.) until there are no longer extreme weights.

- 2. It may not be possible to achieve balance between all potential confounders across treatment groups (i.e., ASMD<0.1). Imbalances in baseline characteristics will be addressed with a re-specification of inverse probability weights (e.g., Changing the functional form of the variable or including interaction terms). However, if imbalances remain these will be described along with their potential impact on the outcome estimate(s).
- 3. It may not be possible to model all collected covariates due to sparsity, collinearity, or other factors that can preclude convergence of statistical models. For this reason, the final variables and functional forms of the baseline (L_0) and time-varying (\overline{L}_k) covariate vectors described in the models above will be determined at the time of analysis.
- 4. The time interval of the analysis, denoted 'k', directly influences the dimensionality of the dataset, and concequent computational intensity of the analysis. Particularly, choosing a time interval of one day will greatly increase the number of rows in the analytic data set and, concequently, increase the computation time of nonparametric bootstrap algorithms for standard error estimation. Therefore, if computation times are too great then the time interval of the analysis may be expanded accordingly (e.g., to one week or one month).

9.7.2.2.2.3 Missing Data

Missing data may arise from participants who skip a single survey only, or who are lost to followup (defined as non-responce on two concecutive follow-up surveys). Participants who are lost to follow-up will be censored at 67 days following the opening of their last survey (as participants are allotted 7 days to answer each 30-day survey). Missing data arising from non-response will be addressed using *last observation carried forward*, where the most recent survey responses are "carried forward" under the assumption that participants' treatment and confounder histories did not change during the time spanning from the participant's final response through the period of non-response.

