- 2. Assign each participant to one of the three treatment strategies of interest (see Table 1) based on their self-reported use of prescribed anti-migraine medications in the prior 30 days: participants who used lasmiditan at least once (Lasmiditan Group), participants who used another prescribed acute anti-migraine medication (includes, but is not limited to, triptans, ubrogepant [Ubrelvy], rimegepant [Nurtec], zavegepant [Zavzpret]; see Annex 3 for the complete list) at least once and did not use lasmiditan (Other Acute Medications Group), and participants who did not use any prescribed acute anti-migraine medication

(No Acute Medication Group). The self-reported use of prescribed preventive antimigraine medication will not be considered for treatment group classification.

- 3. Collect and record each participant's self-reported and calculated confounder history prior to their analytic 'time zero' (see Section 9.7 for potential confounders of interest).
- 4. Define follow-up for each participant from analytic 'time zero' until the earliest of the following: outcome event, loss to follow-up (day 67 of non-response, corresponding to non-response on two consecutive surveys), participant withdrawal, deviation from assigned treatment strategy (e.g., treatment switch), loss of eligibility, or administrative end of study (one-year of follow-up).
- 5. Generate a counting-process formatted dataset for this 'nested trial' derived from longitudinal treatment, outcome, and confounder information assessed in Steps 1-4 (see Section 9.7.2.2.2.1 for example data structure).
- 6. Repeat Steps 1-5 above for each sequential calendar day in which participants will be recruited into the survey study.
- 7. Bind all datasets produced in Step 5 by row. This will serve as the analytic dataset for the primary analysis (see Section 9.7.2.2.2.1 for example data structure).

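### The treatment weight and the censoring weight both carry the probability of staying on strategy and are multiplied, so deviation may be weighted twice; the protocol must say which weight handles it

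*Protocol*

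**What the plan says.** Protocol 9.1 (Step 4) ends a participant's follow-up in a nested trial at several events, among them "deviation from assigned treatment strategy (e.g., treatment switch), loss of eligibility, or administrative end of study (one-year of follow-up". A change of treatment is therefore a censoring event. Table 5 appears to code it that way, in its single censor column: participant 3 is censored in trial 8 on treatment 1, then opens trial 9 on treatment 0 with treatment history 1.

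Section 9.7.2.2.2.1 says that the treatment indicator `A_k` "will be constant for a given participant within a given mth trial".

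Section 9.7.2.2.2.2 then defines two weights.

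- **SW^A.** Under the words "stabilised time-varying inverse probability of treatment to weights will be estimated as follows", it is a product over every interval from m to m+t. Its denominator is "the probability of receiving the treatment that the participant actually received at time 'k,' conditional on treatment, baseline covariate, and time-varying covariate histories".
- **SW^C.** It is a product over the same range, and its only stated reason is that "Because participants are censored when they deviate from their assigned treatment strategies, selection bias may result". In words, "the numerator of the weight is the probability of being uncensored in the next interval conditional on treatment history"; the denominator adds baseline and time-varying covariates.

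Each observation "will be weighted by the joint density of the two weights", that is, SW^A times SW^C. Nothing confines SW^A to time zero, and nothing confines censoring in SW^C to causes other than a change of treatment.

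**The concern.** In a nested-trial analysis that censors at deviation, one inverse probability of staying on strategy is needed per interval. It can come from a time-varying treatment weight or from a censoring weight, but not from both. Here both products run over all follow-up intervals, and both can contain it.

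If it enters twice, the weighted population is no longer the one in which nobody deviates. Where a measured time-varying factor such as attack frequency drives both treatment change and accidents, the primary hazard ratio can then be carried past the true value. The weights also become more dispersed. That lowers the effective sample size and makes the percentile truncation listed under the contingencies more likely, in a study that already expects difficulty recruiting lasmiditan users (9.5).

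**Working it through.** The protocol states no switching rate, no covariate effect and no expected weight distribution, so there is no figure to reproduce. The check is algebra on the printed formulas, followed by simulation under assumed inputs.

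**Algebra.** For a participant on strategy a in interval k, let

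- `s_k` = P(A_(k+1) = a | A_k = a, baseline covariates, covariate history to k), the probability of staying;
- `q_k` = P(not lost, withdrawn or ineligible | stayed, same history).

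If a switch sets C = 1, then C_(k+1) = 0 implies A_(k+1) = A_k. Hence:

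1. The SW^C denominator at k is P(C_(k+1) = 0 | ...) = `s_k × q_k`.
2. The SW^A denominator at k+1 is P(A_(k+1) = a | A_k = a, ...) = `s_k`. It conditions on covariates one interval back, so on the same history.
3. The product contains `s_k² × q_k`, where `s_k × q_k` is needed.

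**Which rows.** Whether step 2 takes effect depends on the data used for the treatment model.

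- *Data that contain the switch intervals:* the full double count applies.
- *All rows of the bound dataset (9.1, Step 7):* the time-zero rows of repeat entrants contain switches (Table 5, participant 3, trial 9, k = 0: treatment 0, history 1). SW^A conditions only on no earlier event, so the formula does not exclude these rows. The double count is then partial.
- *Post-baseline rows only:* `A_k` equals `A_(k-1)` throughout, every later factor is 1, and SW^C alone handles deviation.

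**Simulation of the full double count, true hazard ratio 1.00.** Two strategies and 12 intervals. A time-varying covariate raises the outcome log-odds by 0.8 per unit in both groups and drives switching in one group. At the covariate mean, the probability of staying per interval is 0.92 (low switching) or 0.82 (higher switching), and the event risk is about 0.55% per interval. Mantel-Haenszel over intervals, 6 runs of 400,000, no truncation.

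| Covariate effect on switching / switching level | Unweighted | Once | Twice | 99.9th percentile weight, once → twice | Effective sample fraction, once → twice |
|---|---|---|---|---|---|
| Weak / low | 0.93 | 0.99 | 1.08 | 2.2 → 4.9 | 0.98 → 0.89 |
| Weak / higher | 0.88 | 0.99 | 1.17 | 3.8 → 14.5 | 0.93 → 0.22 |
| Strong / low | 0.86 | 0.99 | 1.28 | 5.2 → 26.9 | 0.84 → 0.01 |
| Strong / higher | 0.80 | 0.98 | 1.45 (unstable; Monte Carlo SD of log HR 0.38) | 8.8 → 76.9 | 0.44 → 0.00 |

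**Simulation with a true hazard ratio of 1.99.** Monthly staying probability is 0.65 to 0.90 on lasmiditan and 0.80 to 0.92 on the comparator, depending on attack frequency, and frequent attacks triple the hazard. Results: unweighted 2.25, once 1.99, twice 1.76. Here the double count moves the estimate down; in the table it moves it up.

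**Simulation with the treatment model fitted to the pooled rows.** Fitted post-baseline staying probabilities were about 0.90 to 0.99. Late effective sample size fell from about 59% to 37%, and the hazard ratio moved by about 0.02 to 0.04. With true switching probabilities in place of the fitted ones, the corresponding figures were about 11% and 0.05 to 0.20.

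**Simulation with a fast-changing covariate.** The hazard ratio barely moved (1.90 once, 1.93 twice, within noise), although month-12 effective sample size fell from 69% to 19%.

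**The case against.** The strongest reply is that section 9.7.2.2.2.1 holds `A_k` constant within a trial. In Table 5, treatment and treatment history differ on one row only, and that is a time-zero row. A model fitted to post-baseline rows sees no switch, so SW^A reduces to assignment at time zero and SW^C carries deviation once, which is correct. This stands as one possible reading, but the protocol does not secure it: SW^A is called time-varying, is printed as a product over all intervals, and is not limited to rows without a switch. On that reading most of the printed formula does no work.

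A reader might infer that the primary hazard ratio is certainly over-corrected, or that the weights are simply squared. The documents support neither. The SW^A numerator conditions on baseline covariates and the SW^C numerator does not. SW^C also covers loss, withdrawal and ineligibility. The time-zero SW^A factor is assignment, not staying, and the last SW^C factor has no counterpart in SW^A. Stabilisation and truncation would limit extreme weights. The simulations that apply known staying probabilities twice show what full double weighting does, not that the plan will do it. The 1.99 example also assumes heavy switching: 0.65^12 is about 0.6% and 0.90^12 about 28% still on strategy at one year.

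It is also true that 9.7 defers complete details to the SAP, and that the weighted model runs only if enough lasmiditan users enrol (9.5, 9.7.2.2). However, both formulas and their product are printed in the protocol as the primary analysis, so their overlap is not merely an SAP detail.

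**Conclusion.** The point holds as a defect in the specification of the primary estimator. As written, the weights either count adherence twice, fully or in part, or contain treatment factors that are degenerate after time zero, and the protocol does not say which.

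If there is double counting, weights inflate, effective sample size falls and truncation becomes more likely. The hazard ratio can also be biased. In the simulations the shift ran from negligible (fast-changing covariate), through about 0.02 to 0.04 (pooled rows), to 1.08 to 1.45 against a truth of 1.00, or 1.76 against 1.99 (full double count). These sizes are illustrative. They rest on assumed switching rates and covariate effects, and on a switch being coded as C = 1. Neither size nor direction can be read from the documents. If measured covariates hardly predict switching, the effect is small.

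**What to change.** Weight deviation once, and state which of these is meant:

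- Restrict SW^A to k = m, the assignment at each nested trial's time zero, and let SW^C carry all post-baseline censoring including change of treatment, preferably with separate models for deviation and for loss or ineligibility.
- Or keep SW^A over all k, fitted on data that include the intervals in which switches occur, and define C in SW^C as loss to follow-up, withdrawal and loss of eligibility only.

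In either case, name the rows on which each weight model is fitted. The cost is one formula and a sentence or two in the protocol and SAP, with no new data. It should be settled before comparative results are seen.
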